7.5. Missing Data

Several attempts will be made to contact patients and to limit missing data. Some imputation (e.g., in order to estimate minimum and maximum exposure) may be required. Details on handling of missing data will be included in the statistical analysis plan (SAP).

7.6. Limitations of the Registry

The planned registry offers as strengths the long-term follow-up during and after treatment with etanercept in a population of paediatric psoriasis patients in the EU. Such a setting will allow fulfilment of the objectives of this registry. However, the registry also carries some limitations. As in any registry, lack of an internal ‘untreated’ contemporaneous comparator group may pose some challenges for the interpretation of data. In the evaluation of the risk of serious and pre-specified opportunistic infections, an attempt will be made to make comparisons within the registry population based on current/recent treatment and periods without etanercept treatment. However, such an approach is unfeasible when assessing risk of malignancies and appropriate external comparator groups will be needed to aid in the interpretation of the registry data. Generalizability of the results may be limited by the characteristics of the population that voluntarily enrol in the registry. Attempts will be made

to characterize and compare patients who refuse to participate with patients who agree to enrol in the registry.

The registry will include patients who initiated etanercept prior to enrolment into the registry. There is the possibility that these patients, who must be considered actively treated at the time of enrolment, are substantively different than other patients who were prescribed etanercept at the same time, but did not tolerate therapy or experienced one or more relevant SAEs, potentially resulting in a differential depletion of susceptible (i.e., the effect whereby patients who remain on treatment are those who can tolerate them while those who are susceptible select themselves out of the population at risk). This could lead to an underestimation, or dilution, of the estimated risk of developing an adverse event associated with etanercept in the population with retrospective data collection.

Generalizability of the results may be limited by the characteristics of the population that voluntarily enrol in the registry. Attempts will be made to characterize and compare patients who refuse to participate with patients who agree to enrol in the registry.

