4.2. Inclusion Criteria

To be eligible for registry enrolment, patients must meet all of the following criteria:

- Age ≤ 17 years at time of administration of the first dose of etanercept
- Diagnosis of plaque psoriasis by a dermatologist
- Prior to enrolment, a clinical decision has been made to prescribe etanercept for the treatment of psoriasis
- Newly prescribed with initial etanercept or actively being treated with etanercept, regardless of length of treatment prior to study enrolment
- Capable and willing to provide paediatric assent, or written informed consent when applicable, and
- Parent(s)/legal representative of patient is capable and willing to provide written informed consent

- Evidence of a personally signed and dated informed consent document indicating that the patient (or a legally acceptable representative) has been informed of all pertinent aspects of the study must exist.

Please note: Currently etanercept is approved for the treatment of severe plaque psoriasis in children and adolescents from the age of 6 years who are inadequately controlled by, or are intolerant to, other systemic therapies or phototherapies. The registry protocol will not encourage use of etanercept at younger ages. However if a doctor, in collaboration with the child's parents, makes the independent clinical decision to prescribe etanercept to a child less than 6 years of age for severe plaque psoriasis, that child may be included in the registry.

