6.2. Data Collection

Data collection is designed to minimise the burden on the participating RPs and patients, and maximise retention. Electronic case report form for data entry, are designed to elicit the specific desired data points.

Data will be collected from the following sources:

- Prospective data provided by the treating physicians (this may be multiple physicians including the prescribing dermatologist or RP, and other physicians responsible for the patient's care over the course of the study);
- Prospective data collected from patient interviews during the less frequent follow-up phase of the study.
- Retrospective data collected by medical record abstraction

The RP will provide information on current prescriptions and status of each registry patient at enrolment and at each scheduled follow-up assessment. Following enrolment in the registry, the RP will also provide information by retrieving medical record information at his/her own institution and other health care settings, as appropriate. Some patients may be undergoing active treatment with etanercept at the time of registry enrolment, and the lag between initiating etanercept treatment and active data collection as part of the registry will necessitate the abstraction of relevant safety-related and treatment pattern information from the medical record. The number of patients meeting this criterion is expected to be limited.

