#### **6.5 Planned subgroups**

Descriptive analyses will be stratified, where specified, by:

- Enrollment type: Prospective (i.e., patients who started etanercept within 30 days before the enrollment date or any time after enrollment date) or retrospective
- Treatment period (initial 24 weeks/post 24 weeks/all follow-up)
- Completion of initial 24 weeks of etanercept exposure (yes/no/unknown)

Analysis of outcomes of interest:

- Etanercept exposure status (current/recent or past)
- Infection status (none during follow-up/in association with recent or current exposure/in association with past exposure)

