## 7. Primary and Secondary Analyses

Evaluations and interpretations will be based on point estimates and 95% confidence intervals (CI) as evaluation of the statistical precision around the point estimate, unless otherwise specified. No formal hypothesis testing is planned. This approach follows the *Guidelines for Good Pharmacoepidemiology Practices*, Section D, point 10 [1]. Unless otherwise specified, all listings and tables are based on the total Registry population at the time of data cut-off for analysis.

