### **7.3 Risk of infection associated with etanercept exposure**

The following patient listings will be generated:

- All serious and opportunistic infections
  - Serious (infection site, pathogen, onset date, resolution date or ongoing, date of last etanercept dose prior to infection)
  - Opportunistic (infection type, nosocomial, onset date, resolution date or ongoing, date of last etanercept dose prior to infection)
  - Concomitant therapies (all) within 28 days prior to each infection
  - Immunosuppressant/steroid use within 28 days prior to each infection

In addition, the following tabular summaries will be presented:

- Number of unique patients, total number of events, and incidence rate of all reported serious and opportunistic infections (by MedDRA System Organ Class (SOC) and Preferred Term (PT))
- Overall incidence rate, stratified by exposure type (current/recent and past)
- Overall incidence rate, stratified by treatment period ( $\leq 24$  weeks,  $> 24$  weeks) during any period of etanercept treatment
- Summary of use of other immunosuppressants or steroids within 28 days prior to serious and opportunistic infection
- Summary of baseline characteristics (demographic and clinical characteristics) stratified by infection status (none reported, reported in association with current or recent exposure, reported in association with past exposure, and specifically associated with initial course)
- Summary of number of infections reported per patient (overall and by exposure status)
- If an adequate number ( $\geq 5$ ) of infections are recorded in each of the current/recent and past treatment groups, relative risk (95% CI) of infection will be calculated as the

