### **7.7 Effectiveness of treatment**

Treatment discontinuation for lack of desired therapeutic effect will, for purposes of analysis, serve as a proxy for treatment effectiveness.

A listing will be generated presenting all patients discontinuing the initial course of etanercept which will include reason for discontinuation, duration of initial course and use of previous systemic therapies.

The following summaries will also be presented:

- Summary of proportion of patients who discontinue etanercept early (< 24 weeks) due to lack of effect, AE or intolerance (primary analysis) during any period of etanercept treatment
- Summary of treatment discontinuation among all patients during any period of etanercept treatment, by each reason and in aggregate (primary analysis)
- Summary of baseline characteristics, stratified by completion/non-completion of initial 24 weeks of therapy (primary analysis)
- Summary of proportion of patients who discontinue at > 24 weeks during any period of etanercept treatment due to lack of effect, AE or intolerance (secondary analysis)
- Summary of proportion of patients who have decreased disease severity after treatment with etanercept during any period of etanercept treatment compared to baseline (as a secondary analysis) stratified by completion of initial 24 weeks.

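### Infection, SAE and early-discontinuation results are not split by enrolment type in the SAP text, and on-drug time is counted from first dose although only events during participation count

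*Protocol*

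**What the plan says.** **Who enters.** Protocol 4.2 admits new starters and also patients "actively being treated with etanercept, regardless of length of treatment prior to study enrolment". Protocol 4.1.3 makes patients ineligible if they stopped etanercept for good before their site joined. Protocol 6.2 says of the already-treated group: "The number of patients meeting this criterion is expected to be limited". It gives no figure and no cap.

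**The bias foreseen.** Protocol 7.6 raises the possibility that already-treated enrolees differ from patients who started at the same time but did not tolerate therapy or had a relevant SAE. It adds: "This could lead to an underestimation, or dilution, of the estimated risk of developing an adverse event associated with etanercept". The sentence ends by confining this to the group with retrospective data collection.

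**What the SAP derives and where it uses it.** SAP 6.5 defines "Enrollment type: Prospective (i.e., patients who started etanercept within 30 days before the enrollment date or any time after enrollment date) or retrospective". The lead-in to that list is "Descriptive analyses will be stratified, where specified, by". A separate list for outcomes of interest holds only exposure status and infection status. SAP 7 states that, unless otherwise specified, "all listings and tables are based on the total Registry population at the time of data cut-off for analysis".

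- SAP 7.3 (infections): "Overall incidence rate, stratified by exposure type (current/recent and past"), and by treatment period up to and beyond 24 weeks.
- SAP 7.5 (SAEs): by treatment period only.
- SAP 7.7: "Summary of proportion of patients who discontinue etanercept early (< 24 weeks) due to lack of effect, AE or intolerance (primary analysis"), counted over any treatment period.
- SAP 7.2 (exposure) names prospective patients, and Protocol 7.3 compares baseline data by status at enrolment.

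**Time at risk.** Protocol 7.1 and SAP 4 limit primary analyses to events during participation. SAP 6.6 defines on-drug time for infections and SAEs as the sum over treatment periods of last dose minus first dose, plus 1, plus 28 days. It sets time not at risk, for analysis, as total study follow-up minus that sum.

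**The concern.** Two separate things can lower the reported risk.

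**Selection.** An already-treated enrolee has, by design, remained on drug up to enrolment. Children who stopped early because of intolerance or infection, before their site joined, are not in the registry. If the enrolees who remain have fewer events or fewer early stops, pooling them with new starters lowers the figures. The protocol foresees this, and the SAP derives the variable that would show it, but the outcome sections do not use that variable. A baseline comparison cannot show whether event rates differ.

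**Denominator.** The rule about prospective data restricts events. It does not remove already-treated patients, and nothing in SAP 6.6 removes their time on drug before enrolment. During that time no event could have been counted in the primary analysis.

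The registry is a post-authorisation safety study required as a condition of marketing authorisation, and its main output is incidence rates. An avoidable downward error in those rates matters even though no hypothesis is tested.

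**Working it through.** The documents give no figure to reproduce, so the first step is a reading of the text. The rest are illustrations whose inputs are assumptions unless a source is named.

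**Step 1. Text check.** Of the three result sections SAP 7.3, 7.5 and 7.7, none names enrolment type. SAP 6.3 mentions sensitivity analysis only for missing dates. SAP 8 offers only optional exploratory work, such as strata of cumulative exposure.

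**Step 2. Denominator for one patient.** Assume one continuous course: 52 weeks on drug before enrolment, 104 weeks on after it, then 104 weeks off.

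- On-drug time as SAP 6.6 reads: 52 + 104 + 4 = 160 weeks. From enrolment: 104 + 4 = 108 weeks.
- Off-drug time by the subtraction rule, with follow-up counted from enrolment: 208 − 160 = 48 weeks. Correct: 208 − 108 = 100 weeks.
- The interval formula that SAP 6.6 gives just before the subtraction rule (discontinuation date minus last dose plus 28 days, and so on) yields about 100 weeks. The two expressions therefore disagree for this patient.

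**Step 3. Denominator for the cohort.** Let a share f of patients be like this and the rest have 104 weeks on and 104 off, all after enrolment.

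- Factor on the on-drug rate: 108/(108 + 52f).
- Factor on the off-drug rate: 100/(100 − 52f).
- The factor on the current/past rate ratio is the first divided by the second.

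| f | On-drug rate | Off-drug rate | Rate ratio |
|---|---|---|---|
| 10% | 0.95 | 1.05 | 0.90 |
| 25% | 0.89 | 1.15 | 0.78 |
| 50% | 0.81 | 1.35 | 0.60 |

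If the interval formula is used for off-drug time, only the on-drug factor applies.

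**Step 4. Dilution by selection, person-time correct.** Pooled rate divided by new-user rate = (1 − w) + w·r. Here w is the already-treated share of on-drug time and r is their relative event rate.

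| w | r = 0.3 | r = 0.5 | r = 0.7 |
|---|---|---|---|
| 10% | 0.93 | 0.95 | 0.97 |
| 25% | 0.83 | 0.88 | 0.93 |
| 50% | 0.65 | 0.75 | 0.85 |

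With r = 1 there is no dilution.

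A second model ties r to time on drug. Take the rate in the first 24 weeks (0.46 years) as k times the later rate, with 1.5 later years assumed. The new-user rate is (0.46k + 1.5)/1.96, which is 1.235 for k = 2 and 1.469 for k = 3. Already-treated patients have rate 1. With w = 30% to 50%, the pooled rate is 5.7% to 9.5% low for k = 2 and 9.6% to 16.0% low for k = 3.

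**Step 5. Early discontinuation.** Pooled proportion = p[(1 − f) + f·q], where q is the relative probability of an early stop in already-treated patients.

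- p = 20%, f = 10%, 25%, 50%: 18%, 15%, 10% for q = 0, and 19%, 17.5%, 15% for q = 0.5.
- p = 30%, f = 20%, 40%, 60%, q = 0: 24%, 18%, 12%.

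The q = 0 results are worst cases. The SAP 7.7 summary counts early stops in any course, so a patient enrolled after week 24 can still be counted later.

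**Step 6. Price of the split.** With 60 patients and 20% early stops, the exact 95% interval is 10.8% to 32.3% for all (12/60). It is 9.6% to 34.6% for prospective patients if a quarter are already treated (9/45), and 7.7% to 38.6% if half are (6/30).

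**The case against.** **The protocol does not say the overall result is biased.** A reader might infer that it predicts underestimated risk. It speaks of a possibility, and only for the group with retrospective data. This stands. The step to the pooled figures is an inference from SAP 7's default population.

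**The split may already exist.** The SAP document history (version 4.0) records a column for retrospective patients in the T2, T3 and T4 table series. It would therefore be too strong to say that every one of these results is certainly pooled. But the shells are not in the documents, the same entry records only footnote changes for T5 and T6, and tables were renumbered in version 4.1. The column cannot be confirmed for these results.

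**Part of the early risk is already isolated.** SAP 7.3 and 7.5 stratify at 24 weeks. SAP 7.2 names prospective patients for first-course duration, and SAP 5.3.1 defines completion of the initial 24 weeks only for starts near or after enrolment. This stands, and it covers much of the second model in Step 4. It does not show depletion that persists beyond 24 weeks, and it does not reach the SAP 7.7 primary summary.

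**Early infections in enrolled patients are not lost.** They are abstracted from records and summarised separately. That is correct. What is lost is the patients who stopped before their site joined, and no extra column recovers them.

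**The effect is small against the noise.** Three severe infections in 211 patients over 48 weeks (Protocol 1.1) is about 1.5 per 100 patient-years. Over an assumed 160 to 320 on-drug years that is about 2 to 5 events, so a 6% to 16% dilution is less than one event. This is fair for selection. The denominator error is an avoidable inconsistency, and small counts do not justify it.

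**The sponsor may intend time to start at enrolment.** SAP 7.2 summarises overall treatment from enrolment, and SAP 6.6 describes off-drug time as accrued in the registry. The on-drug formula does not say so.

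**Conclusion.** The point holds in two parts and should be corrected.

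First, the text of SAP 7.3, 7.5 and 7.7 leaves unused a derived variable that bears directly on a bias the protocol foresees. How much this dilutes the results is unknown, because the already-treated share is not given and the protocol expects it to be limited. The rate dilution of about 6% to 16% rests on assumed shares, rate ratios and follow-up, and the planned 24-week strata already show part of it. Early-stop proportions of 24%, 18% or 12% in place of 30% are a worst-case bound and should not be read as an expected result.

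Second, SAP 6.6 read literally counts pre-enrolment drug time without its events. Under the subtraction rule it also takes that time away from off-drug time, if study follow-up runs from enrolment. Both effects push the current/past rate ratio down. In the assumed example the on-drug rate is 5% to 19% low, and the ratio 10% to 40% low, for already-treated shares of 10% to 50%. Patients classed as prospective are affected too, by up to 30 days each.

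A reader might infer that prospective patients should become the sole headline. The documents do not support that: Protocol 2.1.1 and SAP 6.4 define the safety population as all patients with at least one dose, and restricting it costs precision.

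**What to change.** 1. Keep the pooled results. Add infection rates, SAE rates and early discontinuation by enrolment type as a pre-specified sensitivity analysis, and state in the SAP text which tables carry the split.
2. In SAP 6.6, start person-time at the later of first dose and enrolment (delayed entry) for every rate that counts only events during participation. Count total follow-up from the same origin, so that the two expressions for off-drug time agree.

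No new data are needed: first-dose date, enrolment date and enrolment type are already collected or derived. The cost is extra columns, a revised derivation, and wide subgroup intervals at 60 to 80 patients, which the report should acknowledge. Delayed entry corrects the denominator. It does not undo selection, so the limitation in Protocol 7.6 still has to be stated beside the results.

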8. DATA COLLECTION AND DATA MANAGEMENT

8.1. Operations

Each participating site will receive appropriate training, which describes all processes that the RP or representative must understand. The information will outline all processes required for a clinic to become a registry site, enrolling patients, providing follow-up data on enrolled patients, maintaining registry documents or files, reporting adverse events and closing the registry. All site staff who participates in enrolling patients, collecting or entering data for the registry will be required to undergo appropriate training.

8.2. Required Documentation

The RP must provide the Sponsor with the following regulatory documents before enrolling any patients:

- Current signed and dated curricula vitae for the RP and site staff having significant responsibility (i.e., those related to determination of eligibility or safety)
- Copy of the IEC approval letter for the protocol and informed consent. All written information provided to the patient must be approved by the IEC
- Copy of the IEC-approved informed consent document to be used
- Copy of the protocol sign-off page signed by the investigator
- Fully executed site agreement

8.3. Data Entry

All data will be collected and entered by the RP/participating sites directly into the EDC system. All sites will be fully trained on using the on-line data capture system, including

eCRF completion guidelines and help files. Sites will have the ability to add a new record, to search for and modify existing records, to search for patients for whom follow-up is due, to identify records with outstanding queries and to identify records that require signatures.

Data collected by the RP, including data collected from interview of patients or their parents/legal representative will be entered into a validated database. All data entry will be conducted so that errors in data completeness, data validity, and data consistency are minimized. It is the RP's responsibility to ensure the accuracy of the data provided to the registry by any site staff that is trained for registry data collection.

On a regular basis, when analysis is planned and after quality assurance procedures have been completed, the database will be frozen and a dataset created so that no further changes take place and analysis can be implemented.

8.4. Case Report Form

As used in this protocol, the term case report form (CRF) should be understood to refer to either a paper form or an electronic data record or both, depending on the data collection method used in this study.

A CRF should be completed for each included patient. The completed original CRFs are the sole property of Pfizer and should not be made available in any form to third parties, except for authorized representatives of Pfizer or appropriate regulatory authorities, without written permission from Pfizer.

The investigator has ultimate responsibility for the collection and reporting of all clinical, safety and laboratory data entered on the CRFs and any other data collection forms (source documents) and ensuring that they are accurate, authentic / original, attributable, complete, consistent, legible, timely (contemporaneous), enduring and available when required. The CRFs must be signed by the investigator or by an authorized staff member to attest that the data contained on the CRFs is true. Any corrections to entries made in the CRFs, source documents must be dated, initialed and explained (if necessary) and should not obscure the original entry.

In most cases, the source documents are the hospital's or the physician's patient chart. In these cases, data collected on the CRFs must match the data in those charts.

In some cases, the CRF, or part of the CRF, may also serve as source documents. In these cases, a document should be available at the investigator's site as well as at Pfizer and clearly identify those data that will be recorded in the CRF, and for which the CRF will stand as the source document.

